12.6.2.1.1 Confirmatory Analysis

The hypothesis to be tested for each of the secondary BoExp is that the geometric mean level on Day 5 of the BoExp for THS 2.2 is lower relative to CC.

Analysis of the secondary BoExp will be conducted on the natural log scale. In order to test the follow hypothesis

$$\begin{aligned} \text{Null hypothesis (H}_0\text{):} \quad & m_1 \geq m_2 \\ \text{Alternative hypothesis (H}_1\text{):} \quad & m_1 < m_2 \end{aligned}$$

Where m_1 and m_2 are the geometric means of the BoExp levels on Day 5 for THS 2.2 and CC respectively.

The SAS code will be the same as described in Section 12.6.1.1 “Primary Biomarkers of Exposure in 24 hour collection”.

12.6.2.2 Nicotine and Cotinine Concentrations

The change from the Day 0 sample will be calculated for the Day 5 sample closest to 08:00 PM only. The concentrations of nicotine and cotinine will be listed and summarized along with this change. Line graphs of the nicotine and cotinine concentration profiles across all study days showing mean and 95% CI will also be produced.

For nicotine and plasma concentrations the change from baseline (Day 0 sample at 08:00 PM - 09:30 PM) on the Day 5 sample closest to 08:00 PM will be analyzed using an ANCOVA model with terms for baseline (Day 0) concentration, sex, average daily CC consumption over the last 4 weeks as reported during screening and product. No adjustment will be made for multiple comparisons.

The SAS code to be used is shown below:

```
Proc mixed data=_data_;
  Class product sex cigarette_cons time_point;
  Model change from baseline = baseline sex cigarette_cons product;
  Lsmean product / diff alpha=0.05 cl;
  Run;
```

LS means for each product along with the difference (THS 2.2 - CC) and 95% CI will be presented in the tables.

All figures, summaries and analyses will be performed on the FAS only.

The data will be presented in the below outputs, the TFL number refers to the TFL number in the accompanying TFL shell document:

TFL number	Title
FIGURES	
15.1.2.31	Plasma Nicotine Concentrations (ng/mL) Mean and 95% CI – FAS
15.1.2.32	Plasma Cotinine Concentrations (ng/mL) Mean and 95% CI – FAS
TABLES	
15.2.4.36	Descriptive Statistics of Plasma Nicotine Concentrations (ng/mL) – FAS
15.2.4.37	Descriptive Statistics of Plasma Cotinine Concentrations (ng/mL) – FAS
15.2.4.42	Analysis of Change from Day 0 Plasma Nicotine and Cotinine Concentrations at 08:00 PM on Day 5 – FAS
LISTINGS	
15.3.3.4	Listing of Plasma Nicotine Concentrations and Sampling Times
15.3.3.5	Listing of Plasma Cotinine Concentrations and Sampling Times

12.6.2.3 Nicotine and Cotinine Pharmacokinetic Parameters

The parameters C_{peak} , C_{avg} and t_{peak} will be calculated on Day 5 as described in Section 7.2 “**Pharmacokinetic Parameters**”. The data will be listed and summarized for both nicotine and cotinine.

The analysis will compare C_{peak} and C_{avg} on Day 5 between the THS 2.2 and CC arms. An analysis of variance (ANOVA) model will be used with terms for sex, average daily CC consumption over the last 4 weeks as reported during screening and product. No adjustment will be made for multiple comparisons.

The SAS code will be similar to that described in Section 12.6.1.1 “**Primary Biomarkers of Exposure in 24 hour collection**”, with no baseline value being included in the model.

LS means for each product along with the difference (THS 2.2 - CC) and 95% CI will be presented in the tables.

For t_{peak} on Day 5 the comparison between the THS 2.2 and CC arms will be made by the Wilcoxon Rank Sum test using PROC NPARIWAY in SAS.

The data will be presented in the below outputs, the TFL number refers to the TFL number in the accompanying TFL shell document:

TFL number	Title
FIGURES	
15.1.2.31	Plasma Nicotine Concentrations (ng/mL) Mean and 95% CI – FAS
15.1.2.32	Plasma Cotinine Concentrations (ng/mL) Mean and 95% CI – FAS
TABLES	
15.2.4.38	Descriptive Statistics of Plasma Nicotine Concentration Parameters on Day 5 – FAS

TFL number	Title
15.2.4.39	Descriptive Statistics of Plasma Cotinine Concentration Parameters on Day 5 – FAS
15.2.4.40	Analysis of Plasma Nicotine Concentration Parameters on Day 5 – FAS
15.2.4.41	Analysis of Plasma Cotinine Concentration Parameters on Day 5 – FAS
LISTINGS	
15.3.3.4	Listing of Plasma Nicotine Concentrations and Sampling Times
15.3.3.5	Listing of Plasma Cotinine Concentrations and Sampling Times
15.3.3.6	Listing of Plasma Nicotine Concentration Parameters on Day 5
15.3.3.7	Listing of Plasma Cotinine Concentration Parameters on Day 5

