 - THS 2.2 Arm: 80 subjects, ad libitum use of the product.
 - CC Arm: 40 subjects, ad libitum use of their preferred CC brand.
 - SA Arm: 40 subjects who will abstain from smoking.

Subjects will be informed of their randomized study arm by the study site staff on Day 1 prior to 06:30 AM.
- Exposure period (from Day 1, 06:30 AM until Day 5, 11:00 PM):

The exposure period will consist of 5 days of ad libitum use of the assigned product between 06:30 AM and 11:00 PM in THS 2.2 and CC arms. Use of any tobacco/nicotine-containing product other than the assigned product will not be allowed and may, at the discretion of the Investigator or designee, result in the subject withdrawal from the study.

Subjects in the SA arm will be asked to abstain from smoking any nicotine/tobacco-containing product and will not be provided with medication to support SA.

The end of the 24-hour urine collection period for Day 5 will end in the morning on Day 6 prior to Discharge.
- Day of Discharge (Day 6) (from Day 5, 11:01 PM to time of Discharge):

Procedures of Discharge, including but not limited to laboratory parameters, will be conducted to discharge the subject from the clinic after 9 days in a confined setting. Use of CC will be allowed on Day 6, but only after spirometry has been performed.
- Safety follow-up period (from Day 6, time of Discharge to Day 13):

Confidentiality statement: Data and information contained in this document are considered to constitute trade secrets and confidential commercial information, and the legal protections provided to such trade secrets and confidential information are hereby claimed under the applicable provisions of applicable law. No part of this document may be publicly disclosed without the written consent of Philip Morris Products S.A.

After time of Discharge, subject will enter a 7-day safety follow-up during which there will be recording of spontaneously reported new AEs/SAEs and the active follow-up of ongoing AEs/SAEs by the study site. In general, all AEs will be actively followed until resolved, stabilized (i.e., no worsening of the event), or a plausible explanation for the event has been found. The end of study (EOS) is defined as the time of Discharge on Day 6 plus 7-day follow-up period.

During the study, subjects in the CC and THS 2.2 arms who want to quit smoking will receive appropriate medical advice and will be referred to a smoking cessation counselor.

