7.5.1.2 Plasma Nicotine and Cotinine

Nicotine and cotinine concentrations will be measured in plasma to evaluate the exposure to nicotine. For subjects in the SA arm, blood samples will be collected on Day 0 to Day 4, at comparable time points. No nicotine PK profile will be done for subjects in the SA arm on Day 5 and Day 6.

- On Day 0 to Day 4 (all study arms):

One blood sample for nicotine and cotinine will be drawn each day 08:00 PM-10:00 PM.

- Nicotine/cotinine PK profile on Day 5 and Day 6 (THS 2.2 and CC arms only):

In total, 9 blood samples will be drawn on Day 5. The first blood sample on Day 5 will be drawn within 15 minutes prior to the first product use (T0). On Day 5, T0 will serve as a reference for the time to peak concentration. An additional 8 blood samples will be drawn in 2 hour intervals after T0. The last blood sample should be drawn no later than 11:00 PM, corresponding to the end of the product use. At all time points, if the subject wants to smoke around the time of the blood draw, he/she should smoke first and the blood will be drawn after the product has been used. Depending on the time of the first product use, it may be that fewer than 8 blood samples will be collected from a subject after T0.

On Day 6, two blood samples will be drawn. The first sample will be 20 hours after T0 and the second blood sample will be 24 hours after T0 (with T0 being the time of the first product use on Day 5).

- On Day 5 and Day 6 (SA arm only):

On Day 5, one blood sample will be drawn 08:00 PM-10:00 PM.

On Day 6, one blood sample will be drawn 08:00 AM-10:00 AM.

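### SAP 12.6.2.3 compares nicotine and cotinine C_peak and C_avg without the Day 0 plasma concentration as a covariate, probably losing precision that would cost almost nothing to keep

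*SAP*

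**What the plan says.** SAP 12.6.2.3 (Nicotine and Cotinine Pharmacokinetic Parameters) specifies for C_peak and C_avg: "An analysis of variance (ANOVA) model will be used with terms for sex, average daily CC consumption over the last 4 weeks", plus product. It takes its SAS code from SAP 12.6.1.1, "with no baseline value being included in the model".

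Protocol 7.5.1.2 (Plasma Nicotine and Cotinine) says, for Days 0 to 4 and for all three arms: "One blood sample for nicotine and cotinine will be drawn each day 08:00 PM-10:00 PM". The full profile that yields C_peak and C_avg is taken on Days 5 and 6 only, in the THS 2.2 and CC arms only.

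SAP 12.6.2.2, one section before the PK parameters, takes the Day 5 sample closest to 08:00 PM. Its change from the Day 0 sample "will be analyzed using an ANCOVA model with terms for baseline (Day 0) concentration", together with sex, consumption and product.

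The SAP gives no reason for leaving the Day 0 level out of 12.6.2.3.

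**The concern.** In the THS 2.2 and CC arms, the Day 5 evening sample is one point of the curve that C_peak and C_avg summarize. The plan adjusts that point for the subject's Day 0 level but does not adjust the two summaries of the same curve.

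A covariate need not be the same parameter as the outcome. It has to be unaffected by the assigned product and to predict the outcome. The Day 0 evening level meets the first condition: it is drawn before exposure begins at 06:30 AM on Day 1 and before subjects learn their arm. It plausibly meets the second, because a person's level under free smoking reflects individual intake and clearance beyond what sex and reported consumption capture.

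If it does predict the outcome, between-subject variation that could be removed stays in the error term, and the intervals for C_peak and C_avg are wider than the collected data require.

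**Working it through.** **The plan's own figures.** Neither document gives a power or precision figure for C_peak or C_avg. The nearest is the power for the primary biomarkers with the same two arms: 96% for a 50% reduction under the YVD-CS01-EU assumptions (Protocol 12.2, Table 18). It reproduces with sd = √ln(1+CV²), SE = sd·√(1/40+1/80), one-sided 2.5%. For COHb (ratio 0.40, CV 0.32):
- sd = √ln(1.1024) = 0.312; SE = 0.312 × 0.1936 = 0.0605
- ln(0.50/0.40)/SE − 1.96 = 1.73, so power is 0.958

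The other three biomarkers are close to certain to pass, so the product is 95.8%. This confirms the 80 versus 40 basis and nothing more.

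**Inputs for this point**
- 80 subjects in THS 2.2 and 40 in CC (Protocol 4.1). SA subjects have no Day 5 profile, so N = 120.
- Current model: intercept, sex, consumption, product. That is 4 parameters, leaving 116 df, or 115 with one covariate.
- Two-sided 95% CIs (Protocol 12.1.5).
- ρ, the within-arm correlation of the Day 0 level with the outcome after sex and consumption. It is **not in the documents**, so a range is shown.

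**Formula.** Expected CI half-width with the covariate, relative to the planned model:

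√(1−ρ²) × √(1 + 1/(115−1)) × t₀.₉₇₅(115)/t₀.₉₇₅(116)

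The second factor is the cost of chance imbalance in the covariate, √(1+1/114) = 1.0044. The third is almost exactly 1. Equivalent N is 120/(1−ρ²). The power column takes a contrast that has 80% power unadjusted.

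| ρ | √(1−ρ²) | relative CI width | equivalent N | power if 80% unadjusted |
|---|---|---|---|---|
| 0 | 1.000 | 1.004 | 120 | 80% |
| 0.3 | 0.954 | 0.958 | 132 | 84% |
| 0.5 | 0.866 | 0.870 | 160 | 90% |
| 0.7 | 0.714 | 0.717 | 235 | 97.5% |

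Simulation (4,000 runs per value of ρ) gives width ratios of 1.004, 0.958, 0.871 and 0.718. The ratio crosses 1 at ρ = 0.09.

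**Fewer analysable subjects.** SAP 7.2 needs every profile sample to be present, while Protocol 7.5.1.2 expects some subjects to have fewer than eight samples after T0. Eight draws at 2-hour spacing take 16 hours, so finishing by 11:00 PM needs T0 by about 07:00 AM. The analysed number may therefore fall below 120. At 60 versus 30 the ratios for ρ = 0.3, 0.5 and 0.7 are 0.960, 0.871 and 0.719, with break-even at 0.11. At 40 versus 20 they are 0.963, 0.874 and 0.721, with break-even at 0.14. The relative gain barely changes.

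**The case against.** The strongest defence is that no baseline C_peak or C_avg exists, because the profile is taken only on Days 5 and 6. SAP 12.6.2.2 is then not an exact parallel: it pairs like with like at a similar clock time. The Day 0 value is a single evening sample. It was also taken under a different rule: on Day 5 a subject who wants to smoke does so before the draw, whereas on other days procedures take priority (Protocol 6.6.1). In addition, Day 0 reflects cigarettes while Day 5 in the THS 2.2 arm reflects another product, so the slope could differ by arm.

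These points stand as reasons why ρ may be modest, and unequal slopes would reduce the gain shown above. They do not make the adjustment invalid. Nor does the SAP apply the missing-baseline argument consistently: 12.6.2.4 also omits baseline for CYP1A2, although the identical ratio is measured on Day 0.

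Three stronger readings are tempting, and the documents do not support them:
- **That the model has no baseline information.** It contains sex and screening-reported consumption, and the second already carries part of baseline intake. What is missing is a baseline concentration.
- **That nicotine exposure is compared only without baseline adjustment.** The Day 5 evening concentrations (12.6.2.2) and urinary NEQ (12.6.2.1) are both compared with a baseline term. Within 12.6.2.3, t_peak is compared as well, by a rank test.
- **That the covariate costs nothing.** SAP 12.1.5 does not impute missing data in general, so a subject without a Day 0 level would leave the model.

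**Conclusion.** The point holds as an efficiency improvement. The planned ANOVA is not an error: the arms are randomized, so the comparison is unbiased without the covariate, and the four primary biomarkers are unaffected. The objective served is secondary and descriptive, with no hypothesis or success criterion for these parameters.

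The likely loss is CIs for C_peak and C_avg that are wider than they need be. With adjustment they would be about 4% to 28% narrower for ρ from 0.3 to 0.7, against a worst case of about 0.4% wider at ρ = 0. This rests on an assumed ρ, a common slope in both arms and complete Day 0 values. ρ may differ across the four outcomes (two analytes, two parameters). A marginal correlation, not adjusted for sex and consumption, should not be put into the table, because it could overstate the gain.

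**What to change.** In SAP 12.6.2.3, replace the ANOVA for C_peak and C_avg with an ANCOVA that adds the Day 0 evening concentration of the same analyte. Keep sex, consumption and product.

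Put the covariate on the outcome's scale, and state that scale. The section borrows code from 12.6.1.1, which logs the outcome, but reports a difference between products where 12.6.1.1 reports a ratio. If the outcome is logged, log the covariate.

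Identify the Day 0 sample by the protocol window of 08:00–10:00 PM. SAP 12.6.2.2 ends it at 09:30 PM, which could needlessly exclude a valid value. Report how many subjects lack a Day 0 level and so leave the model.

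The cost is one model term and one degree of freedom, with no new samples or visits. Missing Day 0 values would offset some of the gain: for illustration, losing 5 of 120 subjects widens the CI by √(120/115) = 1.02, or about 2%. If the sponsor prefers the ANOVA, one sentence giving the reason would settle the point.

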12.1.5 Significance Level for Inferential Analysis

Unless stated otherwise, all statistical tests will be two-sided and conducted at the 5% level, and all quoted confidence intervals (CIs) will be two-sided 95% CIs.

The primary endpoints will be tested using a multiple testing procedure to preserve the overall alpha level by simultaneously testing the endpoints using a closed procedure with each test performed at an alpha level of 5%. This implies that statistical significance is required for all primary endpoints in order to be able to make confirmatory claims about any of the endpoints.

Full details of this approach will be provided in the SAP.

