6.3 Product Allocation and Blinding

6.3.1 Methods of Assigning Subjects to Product Arms

Randomization will be conducted through the Interactive Web and Voice Response System (IXRS).

Subjects will be randomized to 1 of the 3 arms. Each sex and each of the current CC consumption levels (10-19 CC/day and >19 CC/day) will have a quota applied to ensure they represent at least 40% of the total study population.

Four separate randomization lists were provided (male smokers who smoke 10-19 CC/day, female smokers who smoke 10-19 CC/day, male smokers who smoke >19 CC/day, and female smokers who smoke >19 CC/day). Block randomization is used within each stratum (i.e., each list) in a 2:1:1 ratio (THS 2.2:CC:SA).

The randomization scheme is generated by a statistical division within [REDACTED] and none of the study team (including study sponsor and [REDACTED] investigators and study subjects will be exposed to the live randomization codes prior to randomization.

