**Table 13: Expected Power (YVD-CS01-EU and ZRHX-EX-01 Studies Assumptions)**

Assumptions	Reduction					
	50%	51%	52%	53%	54%	55%
YVD-CS01-EU	96%	91%	85%	75%	63%	48%
ZRHX-EX-01	>99%	>99%	96%	81%	48%	16%

A total of 160 smokers (80 in THS 2.2, 40 in CC, and 40 in the SA arm) will be randomized to demonstrate a reduction of at least 50% on 4 primary BoExp in smokers switching from CC to THS 2.2 as compared to those continuing to smoke CC, using one-sided test with 2.5% type I error probability.

The sample size is sufficient to obtain 95% CIs for the ratio between (geometrical) mean levels of primary BoExp in THS 2.2 and SA with upper and lower limits deviating not more than 18% from the point estimates, with an 80% overall probability of achieving the desired precision of estimating the true mean.

This study has 80% power using a one-sided test with 2.5% type I error probability:

1. To detect a 0.631 [mL/min/kg] (29%) difference between THS 2.2 and CC in CYP1A2 activity, as measured by the CAF clearance, assuming a standard deviation (SD) of 0.564. Effect size and variability are derived from data obtained in the YVD-CS01-EU study sponsored by PMI.
2. To detect a 24.71 [ng/g creatinine] (20%) difference between THS 2.2 and CC in 11-DTX-B2, assuming a SD of 43.78. The anticipated effect size of THS 2.2 is assumed to be about 90% of the effect of smoking cessation.

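### Time to peak nicotine and cotinine is compared by an unstratified Wilcoxon test although randomization is blocked within four strata; the test is valid but loses some power if sex or daily consumption predicts timing

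*SAP*

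**What the plan says.** SAP 6.3.1 sets up the randomization: "Four separate randomization lists were provided", one for each combination of sex and daily consumption (10-19 or >19 CC/day). It adds: "Block randomization is used within each stratum (i.e., each list) in a 2:1:1 ratio (THS 2.2:CC:SA"). Each sex and each consumption level "will have a quota applied to ensure they represent at least 40% of the total study population".

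SAP 12.6.2.3 treats the three Day 5 PK parameters in two ways. For C_peak and C_avg: "An analysis of variance (ANOVA) model will be used with terms for sex, average daily CC consumption over the last 4 weeks", plus product. For t_peak, "the comparison between the THS 2.2 and CC arms will be made by the Wilcoxon Rank Sum test using PROC" NPAR1WAY. No strata, covariates or interval estimate are named for t_peak. SAP Section 9, which lists changes from the protocol's analysis, does not mention a stratified version.

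On error rates, Protocol 12.1.5 applies to t_peak: "Unless stated otherwise, all statistical tests will be two-sided and conducted at the 5" per cent level. The one-sided 2.5% level in SAP Section 8 belongs to the sample-size calculations.

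**The concern.** Blocking within strata makes the THS 2.2 and CC arms nearly identical in their mix of sex and consumption level. Differences between strata therefore add almost nothing to the chance variation of the treatment comparison. The unstratified Wilcoxon test does not use this. Its null variance comes from ranks pooled over all strata and still contains the between-stratum spread, so the statistic varies less under the null than the test assumes. The result is a rejection rate below 5% when there is no difference, and lower power when there is one.

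The SAP's other between-arm models carry both stratification factors, including those for the BoExp, CYP1A2, CYP2A6, risk markers, questionnaires and smoking topography. t_peak is the one between-arm test that drops them, and no reason is given. What is at stake is some sensitivity to a real difference in the timing of the nicotine or cotinine peak.

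**Working it through.** **Plan's own figure.** The documents give no power, effect size, SD or stratum effect for t_peak, so there is nothing to reproduce for this endpoint. As a check that the design is read correctly, take the primary power table (SAP Section 8, 50% column, YVD-CS01-EU assumptions), where COHb drives the result with mean ratio 0.40 and CV 0.32:

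- SD on the log scale = √ln(1 + 0.32²) = 0.312
- SE = 0.312 × √(1/80 + 1/40) = 0.312 × 0.1936 = 0.0605
- ln(0.50/0.40)/0.0605 = 3.69; power = Φ(3.69 − 1.96) = 95.8%, against the stated 96%.

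**Inputs from the documents.** Four strata, blocked 2:1:1 (SAP 6.3.1); 80 THS 2.2 and 40 CC (SAP Section 8); two-sided 5% (Protocol 12.1.5); plasma samples every 2 hours on Day 5 (Protocol 7.5.1.2), hence heavily tied t_peak values.

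**Assumptions.** A product shift of 0.55 SD; a share S of the variance of t_peak lying between strata; equal strata of 20 and 10.

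**Formulas (large-sample, ignoring ties).** Let k = √(1 − S). The Wilcoxon signal is d = 0.55/0.1936 × √(3/π) = 2.84 × 0.977 = 2.776.

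- Actual two-sided error of the unstratified test: 2 × [1 − Φ(1.96/k)]
- 0.55 taken in total SD: unstratified power Φ((d − 1.96)/k), stratified Φ(d/k − 1.96)
- 0.55 taken in within-stratum SD: unstratified power Φ(d − 1.96/k), stratified Φ(d − 1.96)

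At S = 0.20, for example, k = 0.894 and 1.96/k = 2.191. The actual error is 2.8%. With total SD fixed, power is Φ(0.912) = 81.9% against Φ(1.143) = 87.3%. With within-stratum SD fixed, it is Φ(0.584) = 72.0% against Φ(0.816) = 79.3%.

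| Share S | Actual error, unstratified | Power, total SD fixed: unstratified / stratified | Loss | Power, within-stratum SD fixed: unstratified / stratified | Loss |
|---|---|---|---|---|---|
| 0 | 5.0% | 79.3 / 79.3% | 0 | 79.3 / 79.3% | 0 |
| 0.05 | 4.4% | 79.9 / 81.3% | 1.4 | 77.8 / 79.3% | 1.5 |
| 0.10 | 3.9% | 80.5 / 83.3% | 2.8 | 76.1 / 79.3% | 3.2 |
| 0.20 | 2.8% | 81.9 / 87.3% | 5.4 | 72.0 / 79.3% | 7.3 |
| 0.30 | 1.9% | 83.5 / 91.3% | 7.8 | 66.7 / 79.3% | 12.6 |

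**Simulation with the 2-hour grid and tie-corrected variances.** This adds the ties and the small cost of ranking within strata, which the formulas leave out.

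- Total SD fixed (unstratified / van Elteren): share 0, 78.0 / 77.0%; 0.05, 77.8 / 78.6%; 0.10, 78.7 / 81.0%; 0.20, 79.8 / 85.2%; 0.30, 81 / 89%.
- Within-stratum SD fixed, each factor shifting t_peak by 0, 0.25, 0.5, 0.75 or 1.0 SD (shares 0, 0.03, 0.11, 0.22, 0.33): unstratified power 77, 76, 74, 69 and 61%, with type I error 4.9, 4.7, 3.9, 2.7 and 1.7%. Van Elteren power stays at 76 to 77%, with type I error close to 5% throughout.
- Unequal strata at the edge of the 40% quotas (28:14, 20:10, 20:10, 12:6), 0.5 SD per factor: type I error 3.9%, power 74% against 77%.

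Together these give a loss of about 1 point at a 5% share, 2 to 3 at 10%, 5 to 7 at 20% and 8 to 13 at 30%. When the strata explain nothing, the unstratified test is ahead by up to about 1 point.

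**The case against.** The strongest reply is that the planned test breaks nothing. Its error rate is at or below nominal in every setting examined, so a reader who infers bias or false-positive inflation goes further than the calculations allow. Protocol 12.1.1 names the stratification criteria for the primary analysis of the BoExp and does not require them for t_peak. Protocol 12.5.3 plans descriptive summaries for secondary endpoints in general, so a test of t_peak already goes beyond it. The objective is to describe PK profiles. There is no power target, no similarity margin and no multiplicity adjustment for t_peak, and success rests on the four primary BoExp alone (SAP 5.5.2). All of this stands, and it limits the point to a matter of efficiency.

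The size also rests on assumptions. Nothing in the documents says that sex or consumption level predicts when the highest of the 2-hourly samples occurs under ad libitum use, and the 0.55 SD shift is a choice. At a 5% share the loss is close to simulation error. The analysable number may also fall below 80 and 40: SAP 7.2 requires every sample to be non-missing, while Protocol 7.5.1.2 accepts that some subjects will have fewer than eight samples after T0. That affects the absolute power figures and means the balance produced by blocking is not guaranteed among the subjects analysed. It is no argument against comparing within strata.

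A reader might further infer that a conservative test tilts the trial toward declaring the nicotine profiles similar. The documents do not support this. Neither says that a non-significant t_peak will be read as similarity, and the similar profile reported in Protocol 2.1.2 refers to an earlier study of THS 2.1. t_peak is also summarized and listed, so a timing difference would be visible whatever the p-value.

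What remains is an inconsistency within one SAP section that is cheap to remove.

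**Conclusion.** The point holds as a minor efficiency improvement. The t_peak comparison ignores strata that the randomization uses and that the neighbouring C_peak and C_avg models include. The test is valid, and it is conservative only to the extent that sex or daily consumption predicts t_peak. Assuming 80:40, a 0.55 SD shift and a two-sided 5% level, the loss is negligible for weak strata and exceeds about 5 points only when the strata explain roughly 20% or more of the variance, which the documents neither state nor exclude. It would therefore be too strong to say that appreciable power is lost whenever the strata matter at all. No primary conclusion changes.

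**What to change.** In SAP 12.6.2.3, replace the t_peak sentence with: t_peak on Day 5 will be compared between THS 2.2 and CC by the van Elteren (stratified Wilcoxon) test, stratified by sex and daily CC consumption (10-19, >19), using PROC FREQ with CMH2 SCORES=MODRIDIT.

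The cost is one sentence and one line of code, with no new data. The statistical downside is up to about 1 point of power if the strata explain nothing. SAP Section 3 allows amendments until the database is locked; after that, the stratified test can be added and described as a change in the CSR.
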